#### 2.5.2. Exclusion criteria

- Infants transferred to the pediatric ward for advanced treatment
- Infants with a skin rash or other disease that affects the skin where measurements are performed
- Infants that receive or have received phototherapy in the last 24 hours
- Infants with an inborn disease

Newborns that have received phototherapy are excluded, as phototherapy will influence the result of transcutaneous measurements.

#### 2.6. Data collection

Following informed consent, background data such as birth weight, age on examination, gestational age, and type of feeding will be obtained. Gestational age will be based on ultrasound determination and the last normal menstruation period (LNMP). The skin type of the infant will be classified according to the newborn Neomar's scale score (Figure 4).

Transcutaneous bilirubin estimates will be performed over the sternum of the infant. A Dräger Jaundice Meter JM-105 will be used in this study.

Skin reflectance will be done using a CE-marked portable Konica Minolta spectrophotometer CM-700d. The spectrophotometer readings will be used to adjust the existing algorithm from Picterus to African skin and thereafter bilirubin estimates from the taken images will be determined.

The Picterus calibration card will be fixed in place with a disposable back sticker on the newborn's chest with the hole of the card placed over the infant's sternum. A validated smartphone with Picterus JP will then be used to collect digital images, as shown below. Once the phone is aligned with the card, two sets of 6 images of each newborn will be captured, 3 with flash and 3 without flash. After all the images are obtained, a unique ID will be displayed on the smartphone. This ID will be recorded on the case report forms and later used to pair clinical data and digital images.

Fig.5 Picterus JP image procedure

A blood sample to determine TSB will be obtained within 60 minutes of obtaining the images and processed at the Department of clinical biochemistry in the hospital laboratory. In addition, TSB will be measured with neonatal bilirubin analyzer Neo-Bil Plus from DAS to assess the quality of the equipment. For the hospital laboratory analysis, 1 ml of blood is required and will be obtained either by venous puncture or heel prick. An additional 10  $\mu$ l volume of blood will be collected in a heparinized capillary tube for analysis in the Neo-Bil Plus equipment.

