#### 1.2. Problem statement

Picterus performed a pilot study in Uganda from December 2019 to March 2020, which included 167 newborns. Results showed a Pearson correlation index of 0.59 between TSB and the Picterus image estimate, a sensitivity of 66%, and a specificity of 94%, when the cut-off was set to 250  $\mu$ mol/L. Only six newborns had bilirubin levels higher than 250  $\mu$ mol/L. It was concluded that more data is needed to optimize the performance of the tool for dark skin, including spectrophotometric measurements of skin color reflectance and newborns with higher bilirubin levels.

Currently, there is a running project in Uganda where data is collected from newborns with a broader range of bilirubin levels and high melanin content. Additional measurements of skin color reflectance with a spectrophotometer are made to adjust the Picterus JP algorithm and optimize the app performance. However, more data is needed to determine the adequacy of the app. Therefore, collecting data from different populations, such as in Botswana, will be valuable.

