#### 1.7. Justification

We hypothesize that the Picterus JP will offer bilirubin level estimates that are highly correlated to bilirubin levels measured in blood samples in a population in Botswana. Following our hypothesis, the short-term goal for this project is to demonstrate that this screening method can be used to identify children with severe neonatal jaundice independent of skin color. Thus, providing a cheaper, patient-friendly, and more readily available means of neonatal jaundice detection.

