#### 2.3. Study population and sample size calculations

The study population will comprise 150 newborns from the Neonatal Unit and the postnatal ward at Princess Marina Hospital, a number determined by a sample size calculation based on standard errors of the 95% limit agreement, as described by Bland and Alman.

The standard error of the 95% limit of agreement is given by  $\sqrt{\frac{3\times s^2}{n}}$ , where *s* is the standard deviation of the differences between measurements by the two methods, and *n* is the sample size.

The study performed at St. Olav Hospital showed a standard deviation (*s*) of the difference between bilirubin estimates from digital images to blood samples of 35  $\mu$ mol/L.  A sample size (*n*) of 150 participants will then give the confidence interval of the limits of 9,8  $\mu$ mol/L, a relevant size for clinical use.

The study objective of this study is two-folded. First, we wish to determine the correlation between TSB measurement and Picterus image estimate of serum-bilirubin. Second, we wish to determine the accuracy of the Picterus App used as a screening tool.

The study conducted by Aune et al. found an AUC of 0.925. To calculate the sample size for this study we used the used the EasyROC tool, by setting an AUC of 0.9, a significance level of 0.5 and a power to 0.8. This gave the suggested sample size of 12 infants. In order to get a sufficient result for all bilirubin levels, we decided to apply our pilot data to see how many subjects were needed to receive a sample of 12 in three different groups; <100  $\mu$ mol/L, 100-200  $\mu$ mol/L and >200  $\mu$ mol/L. Through this calculation we came to the number of 115 infants.

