#### 2.7.2. Statistical analysis

The bilirubin estimates from the images taken will be determined. The images will be compared to the TSB, NeoBil and TcB measurements using the Pearson correlation coefficient. Sub-analysis for the different skin colors, gestational ages, days of life, and bilirubin levels will be performed for the TSB and image estimate. Sensitivity and specificity analysis will be calculated for different cut-off values using the ROC analysis. Systematic over- or underestimation of bilirubin levels will be evaluated using Bland-Altman plots. To avoid bias, the developer of the product – Picterus AS – will not be involved in statistical work-up or even see the raw data.

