#### Appendix iV: Standard operating procedure

- 1. Obtain written informed consent from the participants.
- 2. Collect background data such as: birth weight, gender, age on examination, gestational age, type of feeding, and Fitzpatrick scale score, newborn Neomar's scale score.
- 3. Using a transcutaneous bilirubinometer Dräger Jaundice Meter JM-105 obtain and record bilirubin estimates.
- 4. Take three measurements of skin reflectance using a CE-marked portable Konica Minolta spectrophotometer CM-700d by placing it on the newborn's chest.
- 5. Place the Picterus Calibration Card on the chest of the newborn with the sticky side facing down and with its hole over the infant's sternum.
- 6. Collect digital images using a validated smartphone with Picterus JP. Once the phone is aligned with the card, capture two sets of 6 images, 3 without flash and 3 with flash.
- 7. Within 60 minutes of obtaining the images, collect a blood sample for TSB estimation and send to the hospital lab for processing.
- Carryout a second TSB measurement with the neonatal bilirubin analyzer Neo-Bil Plus from DAS. Collect10 µl of blood in a heparinized capillary tube for analysis in the Neo-Bil Plus equipment.

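### The algorithm is adjusted with skin readings from the enrolled infants before it is tested in those infants, so no accuracy result comes from a version fixed independently of the test sample

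*Protocol*

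**What the plan says.** - **Adjustment comes first (2.6 Data collection).** "The spectrophotometer readings will be used to adjust the existing algorithm from Picterus to African skin and thereafter bilirubin estimates from the taken images" are to be determined. The adjustment precedes the estimates.
- **Source of the readings (Appendix iV, step 4).** "Take three measurements of skin reflectance using a CE-marked portable Konica Minolta spectrophotometer CM-700d" on the chest of each enrolled newborn.
- **Timing (2.8 Risk assessment).** All image estimates are made after data collection, so no algorithm output is fixed at enrolment.
- **Test (2.7.2 Statistical analysis).** "The images will be compared to the TSB, NeoBil and TcB measurements using the Pearson correlation coefficient". ROC analysis and Bland-Altman plots follow. The developer "will not be involved in statistical work-up or even see the raw data".
- **Role of the two countries (1.2 Problem statement).** Of the running Uganda project: "Additional measurements of skin color reflectance with a spectrophotometer are made to adjust the Picterus JP algorithm and optimize the app performance". Then: "However, more data is needed to determine the adequacy of the app", which is the reason given for collecting data in Botswana.
- **Purpose (1.7 Justification).** "the short-term goal for this project is to demonstrate that this screening method can be used to identify children with severe neonatal jaundice". Section 2.12 describes the study as the first validation work after Uganda.
- **Precision (2.3).** With SD 35 µmol/L, 150 infants "will then give the confidence interval of the limits of 9,8" µmol/L.

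**The concern.** A validation estimate answers the question of how a given, fixed algorithm performs in infants who played no part in shaping it. Here the same 150 infants supply the readings that shape the algorithm and the TSB values against which it is judged. The protocol describes no version locked beforehand, and no result for the unadjusted version. The correlation, limits of agreement, sensitivity and specificity would therefore all describe an algorithm in the sample it was adapted to. A reader of sections 1.7 and 2.12 would take them as performance to be expected in new dark-skinned newborns. Even if the numerical bias is small, the question of how a pre-fixed version performs in this population would go unanswered, although the images needed to answer it are already being collected.

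**Working it through.** **1. The sequence.** Section 2.6 gives readings, then adjustment, then estimates. Appendix iV step 4 shows that the readings come from the participants. Section 2.8 puts the estimates after data collection. Section 2.7.2 tests those estimates against TSB in the participants. Sections 2.3 and 2.5 describe one undivided sample of 150. Read together, the only version with a planned accuracy result is the one adapted to that sample.

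**2. The plan's own precision figure.** SE of a limit = √(3 × 35² / 150) = √24.5 = 4.95 µmol/L. With t on 149 df, 1.976 × 4.95 = 9.78, which rounds to the printed 9,8. (With 1.96 it is 9.70.) The figure reproduces.

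**3. Size if only reflectance is used, as the text names.** The adjustment method is not described, so this is an assumed model and not the developer's method.
- TSB has variance 1, and the image signal is TSB plus error. An unadjusted r of 0.59 (Uganda pilot, 1.2) gives error variance 1/0.59² − 1 = 1.873.
- Half of that error (0.936) is attributed to one skin feature. Further features are noise.
- The signal is residualised on the features in 150 infants without using TSB, then assessed in those infants and in 4,000 new ones.
- The SD of differences depends on how the estimate is scaled. The three scalings are unscaled, variance-matched and shrunk.

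| Features | r, study / new | SD of differences, study ÷ new (unscaled; variance-matched; shrunk) |
|---|---|---|
| 1 | 0.716 / 0.716 | 0.992; 0.995; 0.999 |
| 20 | 0.669 / 0.669 | 0.871; 0.927; 0.987 |

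- At 2, 6 and 12 features the two correlations differ by at most 0.002, and the study value is never the higher one.
- Limits: 1.96 × 35 = ±68.6 µmol/L. If that were seen in the study, new infants would have ±68.7 (68.6/0.999) to ±69.2 (68.6/0.992) with one feature, and ±69.5 (68.6/0.987) to ±78.8 (68.6/0.871) with twenty.
- In the most extreme case the study SD is not itself too narrow (0.967 against a true √0.936 = 0.968). The gap arises because new infants do worse (1.111).
- Sensitivity / specificity in the unscaled model, with a cut-off assumed at 1 SD above mean TSB: one feature, 0.679 / 0.849 in the study and 0.684 / 0.848 in new infants. Twenty features, 0.619 / 0.856 and 0.667 / 0.825. Study sensitivity is not inflated. Specificity is slightly higher at twenty features.

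**4. Size if TSB were an input, which the protocol does not state.** Least squares of TSB on one predictor with r = 0.59 plus k uninformative terms, n = 150, gives r in study / new infants:
- k = 1: 0.592 / 0.585
- k = 5: 0.606 / 0.570
- k = 10: 0.626 / 0.550
- k = 20: 0.660 / 0.518

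For the limits at k = 20, the study SD is about 35 × √(130/150) = 32.6 and the new-infant SD about 35 × √(170/150) = 37.3. The limits are then about ±63.9 and ±73.0, a gap of about 9 µmol/L. This is a scale only. It joins r = 0.59 from Uganda to SD 35 from the earlier hospital study, for which Appendix V gives r = 0.84. Under this model the two imply different TSB SDs: 35/√(1 − 0.59²) = 43 and 35/√(1 − 0.84²) = 65 µmol/L.

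**The case against.** The strongest objection is that skin reflectance is the only input named. An adjustment blind to TSB cannot learn the reference standard, and the calculation above agrees: the correlation hardly moves and sensitivity is not flattered. This stands. A reader might infer that the reported accuracy will be materially inflated, but the documents do not support that. The large gaps need TSB as an input, which is not stated, or many fitted features.

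A second objection is that version control and resampling belong in an analysis plan that is not at hand. That is true of their details. But the protocol itself fixes which version is tested and on whose readings it is adjusted, and an analysis plan written to it would start from estimates already adapted to the sample.

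A third is that adapting the tool to dark skin is part of the purpose. Section 1.2 does call for more data to optimise it, section 1.4 only speaks of investigating its use, and section 2.12 opens with relevance for a potential validation. This softens the conflict. It does not remove it, since sections 1.7 and 2.12 also claim a demonstration and a validation.

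Two further inferences should be resisted:
- Adjusting the developer's algorithm with study readings might look incompatible with the developer not seeing raw data. Section 2.6 names the origin of the algorithm, not who adjusts it, and section 2.7.3 has image analysis done in Denmark with the local principal investigator. No contradiction is shown. The responsible party is simply unnamed.
- The printed 9,8 might look like an error beside 9.70. It agrees with the t-based 9.78.

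**Conclusion.** The point holds as a matter of stated sequence: as written, the study gives no accuracy result for an algorithm version fixed independently of the infants in whom it is tested, yet it is presented as a demonstration and a validation. Confidence in that sequence is high.

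The size of any optimism cannot be derived from the protocol. With reflectance alone it is probably negligible for the correlation. For the limits of agreement it is small: 0.1% to 0.8% in the SD with one feature, and 1.3% to 12.9% with twenty, depending on scaling. A material effect on the correlation would need TSB as an input. All these ranges rest on the assumed models above. The point should be fixed because the remedy is cheap and supplies the missing result, not because a large bias has been shown.

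**What to change.** Amend sections 2.6 and 2.7.2.

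**(a) Independent result.** Record and lock an algorithm version not adjusted on Botswana data (the existing version, or a Uganda-tuned one if available) before TSB is linked to the images. Report its correlation, Bland-Altman limits, sensitivity and specificity on all 150 infants.

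**(b) Adjusted version.** Report the Botswana-adjusted version beside it, labelled as same-sample performance. State that TSB is not an input and that whoever makes the adjustment has no access to TSB. If this version is to support a claim about new infants, repeat the whole adjustment within infant-level cross-validation, whether or not TSB is used.

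**(c) Clarification.** State who makes the adjustment, consistently with sections 2.7.2 (developer and raw data) and 2.7.3 (image analysis in Denmark).

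**Cost.** Protocol wording and one further image-analysis run, plus repeated adjustment in each fold if cross-validated. No extra infants or procedures are needed. All 150 infants serve the independent result, so the planned 9,8 µmol/L is kept. Holding out half instead would give SE √(3 × 35² / 75) = 7.0 and a half-width of 13.9 µmol/L (t, 74 df).

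**Downside.** The independent result may be less favourable (the Uganda pilot gave r = 0.59). The protocol does not confirm that a Uganda-tuned version will be ready. A locked existing version does not itself validate the adjusted one, which is why (b) is needed for any claim about the latter.

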#### 2.7. Data analysis

#### 2.7.1. Laboratory analysis

Total bilirubin levels will be measured at the Department of clinical biochemistry. 1 ml of blood is required for the analysis and can be obtained through venous blood sampling. This will be carried out by the collaborators in the neonatal unit. The analysis is performed on CC- Beckman Coulter AU 680 Analyzer 01. Laboratory equipment is calibrated and maintained according to standard procedures.

#### 2.7.2. Statistical analysis

The bilirubin estimates from the images taken will be determined. The images will be compared to the TSB, NeoBil and TcB measurements using the Pearson correlation coefficient. Sub-analysis for the different skin colors, gestational ages, days of life, and bilirubin levels will be performed for the TSB and image estimate. Sensitivity and specificity analysis will be calculated for different cut-off values using the ROC analysis. Systematic over- or underestimation of bilirubin levels will be evaluated using Bland-Altman plots. To avoid bias, the developer of the product – Picterus AS – will not be involved in statistical work-up or even see the raw data.

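### Does a Pearson correlation with the image estimate leave the Neo-Bil Plus equipment check without an analysis?

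*Protocol*

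**What the plan says.** Protocol section 2.6 sends one blood sample to the hospital laboratory for total serum bilirubin (TSB) and adds a second reading: "TSB will be measured with neonatal bilirubin analyzer Neo-Bil Plus from DAS to assess the quality of the equipment". A further 10 µl is taken for it; the "volume of blood will be collected in a heparinized capillary tube for analysis in the Neo-Bil Plus equipment". Appendix IV repeats the step: "Carryout a second TSB measurement with the neonatal bilirubin analyzer Neo-Bil Plus from DAS".

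Section 2.7.2 names the device once: "The images will be compared to the TSB, NeoBil and TcB measurements using the Pearson correlation coefficient". It limits the sub-analyses by skin colour, gestational age, day of life and bilirubin level to one pair; these "will be performed for the TSB and image estimate". It then adds, without naming a pair, "Systematic over- or underestimation of bilirubin levels will be evaluated using Bland-Altman plots".

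The two specific objectives in section 1.5 concern the image estimate against TSB and TcB, and its accuracy as a screening tool. Neither mentions Neo-Bil. The limits-of-agreement calculation in section 2.3 rests on the standard deviation "of the difference between bilirubin estimates from digital images to blood samples of 35" µmol/L, so it too concerns the image estimate.

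**The concern.** To judge an analyser, one compares it with the reference method, here TSB from the hospital laboratory's analyser. It is not quite clear whether the equipment in section 2.6 means the Neo-Bil Plus or the laboratory analyser, but either reading calls for that same direct comparison. Section 2.7.2 instead pairs Neo-Bil with the image estimate, which is the test under study, and uses a statistic that does not measure agreement.

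Read alone, that sentence suggests that extra blood is drawn from each newborn for a purpose that no named analysis serves. A Neo-Bil Plus that read systematically low could then pass as sound because it correlated with the images as well as laboratory TSB did.

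**Working it through.** **Inputs from the protocol.** n = 150 (sections 2.3 and 2.5). SD of the image-minus-blood difference 35 µmol/L (section 2.3). Image-TSB correlation 0.59 in the Uganda pilot (section 1.2: "Results showed a Pearson correlation index of 0.59 between TSB and the Picterus image estimate") and 0.83 to 0.88 in earlier studies (section 1.1).

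**Assumptions.** The protocol gives no performance data for Neo-Bil. Assumed here: bias of 50 µmol/L or 20%; random error SD e = 20 µmol/L, independent of the image; TSB SD 50 to 80 µmol/L; Neo-Bil minus laboratory difference SD 10 to 30 µmol/L.

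**1. The protocol's own precision figure.** SE of a limit of agreement = √(3 × 35² / 150) = 4.95. Multiplied by t(149) = 1.976 this gives 9.8 µmol/L, as stated in section 2.3. The figure is right, but it is for image versus blood, not for Neo-Bil.

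**2. Systematic error is invisible to the correlation.** Pearson's r does not change when one variable is shifted or multiplied by a positive constant, so corr(image, TSB − 50) = corr(image, 0.8 × TSB) = corr(image, TSB). Yet at a true 250 the readings would be 250 − 50 = 200 and 0.8 × 250 = 200. A simulated data set (TSB mean 170 and SD 65, image error SD 35, Neo-Bil error SD 10) agrees: r(image, Neo-Bil) was 0.876 with no added bias, and still 0.876 with 50 µmol/L added, with readings 30% high, and with readings 30% low.

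**3. Random error is partly visible.** r(image, Neo-Bil) = r(image, TSB) × SD_TSB / √(SD_TSB² + e²). With e = 20 the factor is 0.928 at SD_TSB 50 and 0.970 at SD_TSB 80.

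Both correlations come from the same infants, so the fall has to be judged against the variability of the paired difference between them. The 95% interval of a single r (0.47 to 0.69 for r = 0.59) is not the right yardstick. Simulating the paired difference (4000 runs, n = 150) gives:

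| r(image, TSB) | r(image, Neo-Bil), TSB SD 50 to 80 | Fall | SD of paired difference | Fall in SDs |
|---|---|---|---|---|
| 0.59 | 0.548 to 0.572 | 0.042 to 0.018 | about 0.026 to 0.016 | about 1.7 to 1.1 |
| 0.83 | 0.771 to 0.805 | 0.059 to 0.025 | about 0.019 to 0.012 | about 3.1 to 2.1 |
| 0.88 | 0.817 to 0.854 | 0.063 to 0.026 | about 0.018 to 0.011 | about 3.6 to 2.5 |

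So at 0.83 to 0.88 a random error of this size would often show in the correlations already planned. At 0.59 it usually would not.

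**4. What the planned data give when compared directly.** Half-width of the 95% CI for the Neo-Bil minus laboratory bias: 1.976 × s / √150. For each limit of agreement, by the protocol's formula: 1.976 × √(3s² / 150).

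| s (assumed, µmol/L) | Bias | Each limit |
|---|---|---|
| 10 | ±1.6 | ±2.8 |
| 20 | ±3.2 | ±5.6 |
| 30 | ±4.8 | ±8.4 |

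A bias of 50 µmol/L would be unmistakable. The comparison needs no data beyond what sections 2.6 and 2.7.1 already collect.

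**5. Is the comparison shut out by the text?** No. Section 2.7.2 uses the correlation to relate the images to the three other measurements and does not call it the test of the analyser. The Bland-Altman sentence speaks of bilirubin levels in general, in a paragraph whose list of methods includes TSB, NeoBil and TcB.

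**The case for a change.** The strongest case for a change is that this is more than missing detail. The protocol gives Neo-Bil a purpose and then names one analysis for it, and that analysis cannot serve the purpose. Every pair that section 2.7.2 spells out involves the image estimate, and the only pair with stated limits of agreement is image versus blood, so the natural reading of the Bland-Altman sentence is that it too concerns the image. One added sentence would settle the matter, at no cost in data or procedures, and would fix the equipment check in advance.

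Much of this stands. The named correlation cannot reveal a constant or proportional Neo-Bil error, and no sentence expressly pairs Neo-Bil with laboratory TSB. It does not follow that the plan is wrong. The agreement method is already in section 2.7.2 and its pairs are left open. Choosing them commonly falls to the statistical analysis plan, which is not available here. Anyone holding two bilirubin readings per infant, and told that one was taken to check equipment, would plot one against the other. Limiting the sub-analyses to TSB and the image estimate matches the objectives and is not a sign of neglect.

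**Conclusion.** The observation about the correlation is correct, but it does not call for a change. The gap is which pairs receive a Bland-Altman plot, and analysts would fill it sensibly with data already planned. Leaving it open alters nothing in the image-TSB analyses, the sensitivity and specificity analysis, either specific objective or the sample size of 150.

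The blindness to constant and proportional error is exact and needs no assumption. The claim that random error would also go unseen holds only in part: for an error SD of 20 µmol/L the fall in r is about 1.1 to 1.7 paired SDs at r = 0.59, but about 2.1 to 3.6 at r = 0.83 to 0.88. These figures, and the ±1.6 to ±4.8 µmol/L precision for the bias, rest on assumed spreads and on complete pairs in all 150 infants. The conclusion also assumes that the team makes the direct comparison that its stated purpose implies. A sentence naming that pair would be a courtesy to the reader and not a correction.
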